5.4.2 Supportive Care Guidelines for Cabozantinib-Related Toxicities

The side effect profile of cabozantinib includes GI symptoms (such as nausea, vomiting, and diarrhea, mucositis/stomatitis), fatigue/asthenia, anorexia, weight loss, skin disorders including PPE syndrome, elevated liver function tests (including ALT and AST), increased pancreatic enzymes with rare cases of overt pancreatitis, thyroid function disorders, as well as side effects associated with inhibition of VEGF signaling. The latter of these include arterial and venous thrombotic events such as deep vein thrombosis (DVT), pulmonary embolism (PE), transient ischemic attack, and myocardial infarction, hypertension, hemorrhagic events, proteinuria, wound complications, and rare cases of GI perforation, fistulae formation and rectal/perirectal abscess, osteonecrosis, and reversible posterior leukoencephalopathy (RPLS).

• Gastrointestinal Disorders:

- o Diarrhea
 - Subjects should be instructed to notify their physician immediately at the first signs of poorly formed or loose stool or an increased frequency of bowel movements.
 - Administration of anti-diarrheal/ anti-motility agents is recommended at the first sign of diarrhea as initial management. Some subjects may require more than one antidiarrheal agent.
 - When therapy with antidiarrheal agents does not control the diarrhea to tolerable levels, cabozantinib treatment should be temporarily interrupted or dose reduced. Treatment may resume when acceptable per investigator decision.

- In addition, general supportive measures should be implemented including continuous oral hydration, correction of fluid and electrolyte abnormalities, small frequent meals, and stopping lactose-containing products, high fat meals, and alcohol.
- If diarrhea is high grade or persistent, treat as per diarrhea/colitis related to pembrolizumab.
- Nausea and vomiting
 - Antiemetic agents are recommended as clinically appropriate at the first sign of nausea and vomiting or as prophylaxis to prevent emesis, along with supportive care according to clinical practice guidelines.
 - The 5-HT3 receptor antagonists are recommended over chronic use of NK-1 receptor antagonists and dexamethasone (NK-1 receptor antagonists can induce or inhibit CYP3A4, and glucocorticoids induce CYP3A4 and thus could lower cabozantinib exposure.
- Stomatitis and Mucositis
 - Removal of local factors should be instituted as indicated, such as modification of ill-fitting dentures and appropriate care of gingivitis.
 - During treatment with cabozantinib, good oral hygiene and standard local treatments such as non-traumatic cleansing and oral rinses (e.g. with a weak solution of salt and baking soda) should be maintained.
 - Local treatment should be instituted at the earliest onset of symptoms.
 - Obtain bacterial/viral culture if oral infection is suspected and treat infection as indicated by local guidelines. When stomatitis interferes with adequate nutrition and local therapy is not adequately effective, dose reduction or temporary withholding of cabozantinib should be considered.

Hepatobiliary Disorders:

- Elevations of ALT, AST, and bilirubin have been observed during treatment with cabozantinib.
- Subjects with elevation of ALT, AST, and/or bilirubin should have more frequent laboratory monitoring of these parameters.
- Whenever possible, concomitant hepatotoxic medications should be avoided or discontinued in subjects who develop increased values of ALT, AST, or bilirubin.

- $\circ~$ Dose reductions of study treatment should be considered in any subject who develops drug-related
 - Grade 2 elevated ALT, AST, or bilirubin lasting longer than 1 week.
 - Grade \geq 3 elevated ALT, AST, or bilirubin.
 - ALT/AST elevations $> 3 \times$ ULN in combination with a bilirubin elevation $> 2 \times$ ULN require permanent treatment discontinuation.

• Hematologic Disorders:

- Complete blood counts with differentials and platelets should be performed regularly.
- Subjects with hematologic toxicities may require additional or more frequent laboratory monitoring of these parameters.
- Febrile neutropenia or evidence of infection associated with neutropenia must be assessed immediately and treated appropriately and in a timely manner according to institutional guidelines.
- Use of granulocyte colony-stimulating factor support for neutrophil recovery is allowed per investigator discretion and in accordance with accepted guidelines after the first incidence of clinically relevant cytopenia.
- Dose reductions or dose interruptions for anemia are not mandated but can be applied as clinically indicated.
- Supportive care such as red blood cell or platelet transfusions may be managed according to institutional guidelines.

• Fatigue, Anorexia, and Weight Loss:

- Common causes of fatigue such as anemia, deconditioning, emotional distress (depression and/or anxiety), nutrition, sleep disturbance, and hypothyroidism should be ruled out and/or these causes treated according to standard of care.
- \circ Dose reduction of cabozantinib should be considered when general or pharmacological measures have not been successful in reducing symptoms. Dose interruption may be considered for Grade \geq 3 fatigue despite optimal management, at the investigator's discretion.
- Anorexia and weight loss should be managed according to local standard of care including nutritional support.

• Skin Disorders:

- Palmar-plantar erythrodysesthesia syndrome (also known as hand-foot syndrome), skin rash (including blisters, erythematous rash, macular rash, skin exfoliation, dermatitis acneiform, and papular rash), pruritus, dry skin, and erythema have been reported in cabozantinib-treated subjects.
- All subjects on study should be advised on prophylactic skin care.
- $\circ\,$ Subjects with skin disorders should be carefully monitored for signs of infection.
- Early signs of hand-foot syndrome could be tingling, numbness, and slight redness or mild hyperkeratosis. Early manifestations include painful, symmetrical red and swollen areas on the palms and soles.
- Aggressive management of symptoms is recommended, including early dermatology or podiatry referral.

| CTCAE v4.0 Grade | Action To Be Taken |
|------------------|---|
| 1 | Cabozantinib treatment may be continued at the current dose if PPE is clinically insignificant and tolerable. |
| | If clinically significant or intolerable, cabozantinib should be interrupted and/or reduced to the next lower dose level. |
| | Start urea 20% cream twice daily and clobetasol 0.05% cream once daily. Reassess weekly. Reassess at least weekly; if PPE worsens at any time or does not improve after 2 weeks, proceed to the intervention guidelines for Grade 2. |
| 2 | Cabozantinib treatment may be continued if PPE is tolerated. |
| | Cabozantinib should be dose reduced or interrupted if PPE is intolerable. |
| | Continue urea 20% cream twice daily and clobetasol 0.05% cream once daily and add analgesics (e.g., NSAIDs/GABA agonists) for pain control if needed. |
| | Reassess at least weekly; if PPE does not improve within 2 weeks or worsens or affects self-care, proceed to the intervention guidelines for Grade 3. |

Table 7:Management ofCabozantinib-Related Palmar-PlantarErythrodysesthesia (PPE) Syndrome

| 3 | Interrupt cabozantinib treatment until severity decreases to Grade 1 or Grade 0. |
|---|---|
| | Continue treatment of skin reaction with clobetasol 0.05% cream twice daily and analgesics. |
| | Resume cabozantinib at reduced dose if PPE recovers to Grade 0 or 1. |
| | Discontinue cabozantinib treatment if intolerable PPE recurs after dose reduction or does not improve within 6 weeks. |

• Hypertension:

• Blood pressure should be monitored at each visit.

| Blood pressure or Condition | Action to be Taken |
|--|---|
| SBP 150-160 or DBP 100-110 mmHg | Optimize antihypertensive treatment by adding new or additional antihypertensive medications and/or increase dose of existing medications. |
| | Reduce cabozantinib treatment by one dose level if optimal antihypertensive therapy (usually to include 3 agents) does not result in BP < 150 mm Hg systolic or < 100 mm Hg diastolic. |
| | If subject is symptomatic, interrupt study treatment. |
| SBP > 160 or DBP > 110 mmHg | If optimized antihypertensive therapy (usually to include 3 agents) does not result in $BP < 150 \text{ mm Hg}$ systolic or $< 100 \text{ mm Hg}$ diastolic, cabozantinib treatment should be dose reduced further or interrupted. |
| | Interrupt cabozantinib treatment if upper limits of BP ($\geq 160 \text{ mm Hg}$ systolic or $\geq 110 \text{ mm Hg}$ diastolic) are sustained and not adequately manageable or if BP is > 180 mm Hg systolic or > 120 mm Hg diastolic or if subject is symptomatic. Restart cabozantinib treatment at the most tolerable dose and re-escalate cabozantinib dose only if BP falls to and is sustained at < 140 mm Hg systolic and < 90 mm Hg diastolic. |
| Hypertensive crisis or hypertensive encephalopathy | Discontinue cabozantinib treatment. |

Table 8: Management of Cabozantinib-Related Hypertension

• Thromboembolic Events:

- Subjects who develop a PE or DVT should have cabozantinib treatment held until therapeutic anticoagulation with heparins (e.g., LMWH) is established.
- o Cabozantinib treatment may be resumed in subjects who are stable and have

uncomplicated PE or DVT and are deriving clinical benefit from cabozantinib treatment.

- Subjects with life-threatening PE or DVT should have study treatment discontinued unless toxicity can be managed and subject is deriving clear clinical benefit as determined by the treating physician and agreed by the Principal Investigator.
- Cabozantinib treatment should be discontinued in subjects who develop an acute myocardial infarction or any other clinically relevant arterial thromboembolic complication.

• Proteinuria:

○ If urinalysis shows proteinuria \ge 3+, obtain spot urine protein creatinine ratio.

| Severity of Proteinuria (UPC Ratio) | Action to be Taken | | | | |
|---|---|--|--|--|--|
| UPC Ratio ≤ 1 | No change in cabozantinib treatment or monitoring. | | | | |
| UPC Ratio > 1 to < 3.5 | No change in cabozantinib treatment required. | | | | |
| | Consider confirming with a 24-hour protein assessment within 7 days. Repeat UPCR within 7 days and once per week. If UPCR < 1 on 2 consecutive readings, UPCR monitoring can revert to protocol-specific times. | | | | |
| UPC Ratio ≥ 3.5 | Hold cabozantinib treatment pending repeat UPCR within 7 days and/or 24-hour urine protein. | | | | |
| | If \geq 3.5 on repeat UPCR, continue to hold cabozantinib treatment and check UPCR every 7 days. If UPCR decreases to < 2, restart cabozantinib treatment at a reduced dose and monitoring of urine protein/creatinine should continue weekly until the UPCR decreases to < 1. | | | | |
| Nephrotic syndrome (e.g. proteinuria > 2 grams/day on 24 hour urine or urine protein creatinine ratio >3.5 AND serum albumin < 2 mg/dL AND edema) | Discontinue cabozantinib treatment. | | | | |

Table 9: Management of Cabozantinib-Related Proteinuria

• Hypophosphatemia:

- Serum phosphorus should be monitored frequently while receiving cabozantinib.
- Mild to moderate hypophosphatemia should be managed by oral replacement including food that are high in phosphate (diary items, meats, beans) and/or oral phosphate supplements according to standard clinical practice guidelines.

• Thyroid Function Disorders:

- Changes in thyroid function tests (TFTs) and hypothyroidism have been reported with cabozantinib and other tyrosine kinase inhibitor treatment as a result of altered thyroid hormone regulation.
- Management of thyroid dysfunction (e.g., symptomatic hypothyroidism) should follow accepted clinical practice guidelines.

• Hemorrhagic Events:

• Discontinue cabozantinib treatment in subjects who have been diagnosed with a severe bleeding complication.

• GI Perforation/Fistula and Non-GI Fistula Formation:

- Carefully monitor for episodes of abdominal pain, especially in subjects with known risk factors for developing GI perforation/fistula or non-GI fistula, to allow for early diagnosis.
- Discontinue cabozantinib treatment in subjects who have been diagnosed with GI or non-GI perforation/fistula.

• Osteonecrosis of the Jaw:

- Osteonecrosis of the jaw (ONJ) has been reported with use of anti-angiogenic drugs and bisphosphonates and denosumab in cancer subjects.
- Subjects with any documented case of osteonecrosis should have study treatment discontinued, and appropriate clinical management should be initiated.

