5.2.1.4 Cabozantinib

See Sections 2.1.1 to 2.1.6 for dosing of cabozantinib during the DLT assessment window in Phase I dose escalation.

Dose modification criteria for cabozantinib outside the DLT assessment window and in the dose expansion stage are shown in Table 4. Dose reductions and/or interruptions should be implemented for unacceptable toxicity. Dose modifications or interruptions may also occur in the setting of lower grade toxicity than defined in Table 4, if the investigator feels it is in the interest of the subject's safety and will optimize drug tolerability.

| CTCAE v4.0 Grade | Recommended Guidelines for Management |
|---|---|
| Grade 1 AEs | Add supportive care as indicated. |
| | Continue cabozantinib treatment at current dose level if AE is manageable and tolerable. |
| Grade 2 AEs which are tolerable and are easily managed | Continue cabozantinib treatment at current dose level with supportive care. |
| Grade 2 AEs which are intolerable and cannot be adequately managed | At the discretion of the investigator, cabozantinib should be dose reduced or interrupted until symptoms become more tolerable or are better managed. |
| Grade 3 AEs (except clinically non-relevant laboratory abnormalities) | Hold cabozantinib treatment and optimize supportive care. |
| | Once AE improves to \leq Grade 2 and is tolerable and manageable, resume cabozantinib: |
| | • At same dose if first occurrence of Grade 3 AE despite optimal supportive care. |
| | • At one dose reduction (decrease by 20mg/day) if second occurrence of Grade 3 AE despite optimal supportive care. |
| | Permanently discontinue cabozantinib if third occurrence of Grade 3 AE despite optimal supportive care. |
| Grade 4 AEs (except clinically non-relevant laboratory abnormalities) | Hold cabozantinib treatment immediately. |
| | Discontinue cabozantinib permanently UNLESS the following criteria are met: Subject is deriving clear clinical benefit as determined by the investigator and agreed by the Principal Investigator. |
| | • Toxicity can be managed with a dose reduction following recovery to Grade 1 (or baseline) and optimal medical care. |

Table 4: Dose Modification Guidelines for Cabozantinib Drug-Related Adverse Events

Cabozantinib should be permanently discontinued for any of the following:

- Development of visceral perforation or fistula formation
- Severe hemorrhage
- Serious arterial thromboembolic event (e.g., myocardial infarction, cerebral infarction)

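### After a first Grade 3 PPE, Table 4 restarts cabozantinib at the same dose and Table 7 at a reduced dose, and no text says which table governs

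*Combined protocol and SAP*

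**What the plan says.** Section 5.2.1.4 names one table as the source of the cabozantinib dosing rules: "Dose modification criteria for cabozantinib outside the DLT assessment window and in the dose expansion stage are shown in Table 4". The scope of that table's Grade 3 row is "Grade 3 AEs (except clinically non-relevant laboratory abnormalities", and it lists no other exception. In that row cabozantinib is held. Once the event is at or below "Grade 2 and is tolerable and manageable, resume cabozantinib": "At same dose if first occurrence of Grade 3 AE despite optimal supportive care". A second occurrence restarts 20 mg/day lower. For the next one the instruction is "Permanently discontinue cabozantinib if third occurrence of Grade 3 AE despite optimal supportive care".

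Section 5.4.2, under skin disorders, has its own table for PPE (Table 7). Its Grade 3 row says "Interrupt cabozantinib treatment until severity decreases to Grade 1 or Grade 0", then "Resume cabozantinib at reduced dose if PPE recovers to Grade 0 or 1", and finally "Discontinue cabozantinib treatment if intolerable PPE recurs after dose reduction or does not improve within 6 weeks". It does not distinguish a first occurrence from a later one.

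Table 4 does not mention PPE or Table 7, and Table 7 does not mention Table 4.

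**The concern.** Grade 3 PPE falls inside Table 4 by that table's own scope and is also the subject of a dedicated row in Table 7. For a first occurrence the two rows prescribe different restart doses. Two investigators who each follow the protocol as written could therefore restart the same subject at different doses.

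The protocol anticipates the event: Section 2.1.2 gives Grade 3 hand-foot syndrome, the same condition as PPE, its own DLT exception.

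Two things are at stake. One is the subject's safety on restarting a drug that has just caused a Grade 3 skin toxicity. The other is how dose data are read. Section 8.2.2 plans summaries of exposure and a listing of events leading to treatment discontinuation, and Section 10.6.1 puts dose modifications in the progress report to the monitoring committee. Some of those reductions and stops could reflect which table was consulted rather than how well the drug was tolerated.

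**Working it through.** The protocol states no figure to reproduce on this point, so the check sets the two rows side by side for cabozantinib-related Grade 3 PPE outside the DLT window.

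| Step | Table 4 (5.2.1.4) | Table 7 (5.4.2) | Can both be met? |
|---|---|---|---|
| On onset | Hold | Interrupt | Yes |
| Recovery needed to restart | Grade 2 or lower, tolerable and manageable | Grade 1 or 0 | Yes, by waiting for Grade 1 |
| Restart dose, first occurrence | Same dose | Reduced dose | **No** |
| Permanent stop | Third Grade 3 occurrence | Intolerable recurrence after a reduction, or no improvement in 6 weeks | Mostly follows from the row above |

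**Restart dose.** The step size in Table 4 is 20 mg/day, and the dose levels in Section 2.1.1 are 20, 40 and 60 mg. Table 7 gives no step size, so one 20 mg step is assumed.
- Subject on 60 mg: Table 4 gives 60 mg; Table 7 gives 60 − 20 = 40 mg. Difference 20/60 = 33%.
- Subject on 40 mg: Table 4 gives 40 mg; Table 7 gives 40 − 20 = 20 mg. Difference 20/40 = 50%.

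**Stopping rule.** Under Table 4 the sequence is same dose, one reduction, stop. Under Table 7 it is one reduction, then stop if intolerable PPE returns. Both allow one reduction before the stop. Table 7 can reach the stop one occurrence earlier because it reduces one occurrence earlier. This is largely the restart-dose conflict carried forward, not a separate one.

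**Search for a ranking.** Sections 5.2.1.2, 5.2.1.4, 5.2.1.4.2, 5.4.1 and 5.4.2 contain no PPE exception to Table 4 and no statement that a toxicity-specific table overrides it.

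**Illustration only, on assumed inputs.** Suppose onset on Day 22, an equal hold of h days under both tables, and no further hold or reduction to Day 63. The share of planned cabozantinib received is:
- Table 4: (63 − h)/63, which is 56/63 = 88.9% for h = 7 and 49/63 = 77.8% for h = 14.
- Table 7 from 60 mg: (21×60 + (42 − h)×40)/(63×60), which is 2660/3780 = 70.4% and 2380/3780 = 63.0%.
- Table 7 from 40 mg: (21×40 + (42 − h)×20)/(63×40), which is 1540/2520 = 61.1% and 1400/2520 = 55.6%.

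The documents give no rate of Grade 3 PPE. Over an assumed 2% to 15% in 38 Phase II subjects, the expected number is 38 × 0.02 = 0.8 to 38 × 0.15 = 5.7. The chance of at least one case, 1 − (1 − p)^38, runs from 54% to 99.8%. Onset, hold lengths and rates are all assumed. The Table 4 line also assumes full dose to Day 63 without relapse, which widens the gap. The conclusion does not rest on these figures.

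**The case against.** The strongest reply is that the specific table naturally governs. Section 5.4.2 gives cabozantinib dose instructions toxicity by toxicity, for hypertension and proteinuria as well as PPE, so the structure looks like one general table plus specific modules. Table 4 presents its content as recommended guidance, whereas the text below Table 5 makes dose changes mandatory for events related to both drugs. Section 5.2.1.4 also allows modification for toxicity of lower grade than Table 4 defines. Since PPE is at Grade 2 or lower on restart, an investigator who reduces can claim compliance. And Section 5.2.1.2 has the Principal Investigator notified when one agent is held or modified alone.

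Much of this stands. Specific-over-general is the natural reading, and notification limits how far practice could drift. But the protocol never states that order, Section 5.2.1.4 names Table 4 as the criteria without excepting PPE, and the latitude permits a reduction without settling whether one is due.

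A reader might infer more than the text supports:
- *Three independent contradictions.* The thresholds can be reconciled, because interruption is allowed at the investigator's discretion and waiting for Grade 1 meets both. The stopping rules differ mainly through the restart dose.
- *The text makes Table 4 govern.* The note under Table 5 does send readers there, but only for events first handled under Table 5 and later attributed to a single drug.
- *The RP2D would be distorted.* Section 2.1.5 bases the initial choice on DLT counts and sets no reduction or discontinuation threshold for amending it later. An effect there is speculative.

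**Conclusion.** The inconsistency is real and its severity is low. It comes down to one instruction: the cabozantinib dose on restarting after a first Grade 3 PPE outside the DLT window. The size is one dose level, 33% at 60 mg and 50% at 40 mg, on the assumption that Table 7's reduction is one 20 mg step. From a second occurrence Table 4 reduces as well, so a direct clash of restart doses is confined to the first.

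The consequences are for subject safety and for the consistency of dose-reduction, exposure and discontinuation data. How many subjects would be affected cannot be known from the documents. A reader might infer that the efficacy conclusion is at risk; nothing supports that, since the ORR test, its error rates and the decision rule do not depend on either table.

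**What to change.** Make the PPE-specific table govern. Add after Table 4: *For Grade 3 PPE, the restart threshold, restart dose and discontinuation rule in Table 7 apply in place of Table 4.* The Grade 1 and Grade 2 rows of Table 7 stay as they are.

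The cost is one sentence at the next amendment and a note to sites, with no added visits, tests or subjects. The downside is clinical: some subjects will restart later and at a lower dose than Table 4 would have allowed, and may reach permanent discontinuation one occurrence sooner. That is the more cautious choice after a Grade 3 skin toxicity, and it gives every investigator the same rule.

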ii. Uncontrolled hypertension defined as sustained BP > 150 mm Hg systolic or > 100 mm Hg diastolic despite optimal antihypertensive treatment.

iii. Stroke (including TIA), myocardial infarction, or other ischemic event, or thromboembolic event (e.g., deep venous thrombosis, pulmonary embolism) within 3 months before randomization.

b. Gastrointestinal (GI) disorders including those associated with a high risk of perforation or fistula formation:

i. Tumors invading the GI-tract, active peptic ulcer disease, inflammatory bowel disease, diverticulitis, cholecystitis, symptomatic cholangitis or appendicitis, acute pancreatitis or acute obstruction of the pancreatic or biliary duct, or gastric outlet obstruction.

ii. Abdominal fistula, gastrointestinal perforation, bowel obstruction, or intra-abdominal abscess within 6 months before randomization. Complete healing of an intra-abdominal abscess must be confirmed before study initiation.

c. Has clinically significant hematuria, hematemesis, or hemoptysis of > 0.5 teaspoon within 3 months before randomization.

- d. Known endobronchial disease manifestation. Patients with suspected endobronchial disease on imaging who have no evidence of endobronchial disease on bronchoscopy are allowed. Patients with treated endobronchial disease are also allowed provided they are stable.
- e. Lesions invading major pulmonary blood vessels.
- 20. Has a history or current evidence of any condition, therapy, or laboratory abnormality that might confound the results of the trial, interfere with the subject's participation for the full duration of the trial, or is not in the best interest of the subject to participate, in the opinion of the treating investigator.
- 21. Has known psychiatric or substance abuse disorders that would interfere with cooperation with the requirements of the trial.
- 22. Is pregnant or breastfeeding, or expecting to conceive or father children within the projected duration of the trial, starting with the pre-screening or screening visit through 120 days after the last dose of trial treatment.
- 23. Has an inability to swallow tablets or capsules.
- 24. Has a previously identified allergy or hypersensitivity to components of the study treatment formulations.
- 25. Has a known history of Human Immunodeficiency Virus (HIV) (HIV 1/2 antibodies).
- 26. Has known active Hepatitis B (e.g., HBsAg reactive) or Hepatitis C (e.g., HCV RNA [qualitative] is detected).

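### Table 8's blood pressure control test joins its two limits with 'or', so read literally it calls for a cabozantinib dose step only when both pressures stay high

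*Combined protocol and SAP*

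**What the plan says.** Table 8 in Section 5.4.2 sets out how cabozantinib-related hypertension is handled. Row 1 is headed "SBP 150-160 or DBP 100-110 mmHg" and row 2 "SBP > 160 or DBP > 110 mmHg", so either pressure alone places a subject in a row.

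Both rows start from optimised antihypertensive treatment and then apply the same control test. Row 1: "Reduce cabozantinib treatment by one dose level if optimal antihypertensive therapy (usually to include 3 agents) does not result in" the target pressure. Row 2: if the same target is missed, "cabozantinib treatment should be dose reduced further or interrupted". In both cells the step depends on therapy that "does not result in BP < 150 mm Hg systolic or < 100 mm Hg diastolic".

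Other limits bear on the same question:

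- Row 1 also interrupts treatment in a symptomatic subject.
- Row 2 has a separate interruption rule. It applies at 160 systolic or 110 diastolic and above if this is sustained and cannot be adequately managed, above 180 or 120, or if the subject is symptomatic.
- After interruption the instruction is to "re-escalate cabozantinib dose only if BP falls to and is sustained at < 140 mm Hg systolic and < 90 mm Hg diastolic".
- Exclusion criterion 19.a.ii in Section 5.1.2 reads "Uncontrolled hypertension defined as sustained BP > 150 mm Hg systolic or > 100 mm Hg diastolic despite optimal antihypertensive treatment".

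**The concern.** The control test describes success, not failure. When two limits that define success are joined by 'or', meeting one is enough. A subject can therefore enter row 1 on systolic pressure alone, show no improvement on three agents, and still pass because the diastolic pressure was never high.

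This is the stated dose-reduction trigger for a toxicity that Section 5.4.2 itself lists among the effects of VEGF inhibition. The table exists to give investigators a common rule. As worded, the sentence supports two opposite actions for the same subject. Because "Blood pressure should be monitored at each visit", the question comes up repeatedly, and a literal reader reaches the same answer each time the pattern is unchanged. What is at stake is consistent safety management of isolated systolic or isolated diastolic elevation. No statistical figure in the plan depends on it.

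**Working it through.** The plan gives no figure to reproduce; the check is one of logic.

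**Inputs.** Let S and D be systolic and diastolic pressure on optimal therapy. Row headings, control tests, the row 2 interruption rule and the re-escalation rule come from Table 8. The eligibility definition is exclusion 19.a.ii.

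**Step 1: what the test says.**

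- As written: step due if NOT (S < 150 or D < 100), which equals S ≥ 150 and D ≥ 100.
- With 'and': step due if NOT (S < 150 and D < 100), which equals S ≥ 150 or D ≥ 100.

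The second form has the same structure and lower limits as the row 1 heading. The first does not.

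**Step 2: cases (asymptomatic, on optimal therapy).**

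| BP | Row | Step due as written | Step due with 'and' | Separate Table 8 dose step |
|---|---|---|---|---|
| 145/95 | neither | no | no | none needed |
| 155/85 | 1 | no | yes | none |
| 145/105 | 1 | no | yes | none |
| 155/105 | 1 | yes | yes | none |
| 165/85 | 2 | no | yes | interruption, if sustained and not manageable |
| 145/115 | 2 | no | yes | interruption, if sustained and not manageable |
| 165/115 | 2 | yes | yes | interruption, if sustained and not manageable |

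In each row there are three uncontrolled patterns: systolic only, diastolic only, and both. The literal test fires in 1 of 3, the 'and' test in 3 of 3. These are logical patterns, not proportions of subjects.

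**Step 3: where no other Table 8 step applies.** In row 2, the interruption rule uses either pressure and covers part of the gap. In row 1, the only other dose action is interruption for symptoms. For whole-number readings, the uncovered region is therefore S 150–159 with D < 100, or D 100–109 with S < 150, in an asymptomatic subject.

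**Step 4: consistency with the other limits.** Exclusion 19.a.ii and Table 8 together contain eight paired limits.

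- Five describe pressure that is too high, and all use 'or': exclusion 19.a.ii, the two row headings, 160 or 110 and above, and above 180 or 120.
- Three describe pressure that is controlled. The re-escalation rule uses 'and'; the two control tests use 'or'.

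'Too high' joined by 'or' and 'controlled' joined by 'and' express the same principle: one high pressure is enough to be uncontrolled. Six of the eight follow it. The two control tests are the only ones that let an acceptable pressure offset a high one. For example, a sustained 155/85 despite optimal treatment counts as uncontrolled for eligibility, yet passes the on-treatment test at the same numerical limits.

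**The case against.** The strongest objection is that the sentence need not be read literally. The test repeats the pairing in the row heading, so it can be read respectively: the pressure that put the subject in the row must fall below its own limit. At 155/85 the subject entered on systolic pressure, systolic is not below 150, and the reduction is due. The headings, the re-escalation rule and exclusion 19.a.ii all suggest that this is what was meant. That stands as a reading and probably reflects the intent. It does not remove the literal reading, and the two lead to different actions.

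The second objection is that other provisions may lead to action, and this also stands in part:

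- Section 5.2.1.2 lets the investigator interrupt either drug at any time for adverse events, and Section 5.2.1.4 allows cabozantinib changes below the Table 4 grades.
- Table 4 holds cabozantinib for Grade 3 events, with a 20 mg/day reduction on a second occurrence, and provides for reduction or interruption in intolerable Grade 2 events that cannot be adequately managed. Whether 155/85 on three agents reaches a hold depends on CTCAE v4.0 grading, which Section 12.2 cites but does not reproduce.
- Section 5.2.1.4 lists persistent uncontrolled hypertension despite optimal management as a reason to stop permanently. If the eligibility definition carries over, a persistent 155/85 could fall under it.

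None of these supplies the one-level reduction that row 1 specifies on its own blood pressure trigger. They do limit what can be said about consequences. Table 8 also sits under supportive care guidelines, so its wording guides conduct more than it binds it.

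**Conclusion.** The point holds as a drafting inconsistency in a safety dosing rule, of low severity. Read literally, the control test in rows 1 and 2 fires in one of three uncontrolled patterns, against the protocol's own either-pressure standard elsewhere. The practical gap is mainly row 1, in asymptomatic subjects with isolated elevation. The conclusion rests on the literal reading being one that an investigator could reasonably adopt, and on the intent inferred from the headings, the re-escalation rule and exclusion 19.a.ii.

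Three stronger inferences are tempting but not supported:

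- *That affected subjects receive too much drug.* The dose levels are 20, 40 and 60 mg, so a reader might infer 60/40 = 1.5 or 40/20 = 2 times the intended dose. The documents do not establish a missed step, because discretion, Table 4 or the stop list may intervene. Nor do they allow the number of subjects to be derived.
- *That the permanent-stop bullet in Section 5.2.1.4 conflicts with Table 8.* A graded sequence ending in a stop is the likelier intent. Making that stop depend on Table 8 steps having failed would weaken an unconditional safety criterion, and could be read as also qualifying malignant hypertension and hypertensive crisis in the same bullet.
- *That the trial's conclusions are affected.* DLTs are defined in Section 2.1.2 by CTCAE grade and resolution time, not by Table 8. No effect on RP2D, ORR or the Simon design is claimed.

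**What to change.** In both Table 8 cells (rows 1 and 2), state the target as below 150 mm Hg systolic **and** below 100 mm Hg diastolic, so that the dose step is due whenever either pressure remains at or above its limit. Leave Section 5.2.1.4 as it is.

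The cost is one word in each of two cells, carried in the next amendment. No numerical limit, visit, assessment, sample size or analysis changes.
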